9.8.4. Estimated Glomerular Filtration Rate (eGFR) Assessment

Estimated glomerular filtration rate (eGFR) will be estimated from serum creatinine (Appendix 17.9). The eGFR assessment will be done at Screening (Visit 1), Month 1 (Visit 3), 3 (Visit 5), 6 (Visit 6), 9 (Visit 7), and 12/Discontinuation (Visit 8). Samples taken at the Screening Visit should be split to allow for central laboratory analysis and local laboratory analysis for qualification.

9.8.5. Urinalysis

Standard urinalysis using a dipstick will be conducted for all subjects at the Screening /Qualification Visit (Visit 1) (Table 9.3). The urinalysis will only be done at Screening (Visit 1).

Specific gravity	Blood
pH	RBC
Protein	WBC
Glucose	Bilirubin
Ketones	Urobilinogen

Table 9.3:Urinalysis Determinations

Abbreviations: RBC = red blood cell; WBC = white blood cell.

For samples with positive findings on macroscopic analysis (dipstick), urine microscopic examination for red blood cells, white blood cells, bacteria, and casts should be performed at the central laboratory.

9.8.6. Hepatitis Serology

If a subject discontinues study drug due to confirmed liver enzyme abnormalities or jaundice, the subject will have additional evaluations at the discretion of the Investigator as follows:

- Hepatitis A, B, C, and E screening (anti-HAV IgM, HBsAg, anti-HCV plus viral titer, and evaluation for Hepatitis E),
- Antinuclear antibody (ANA) and anti-SmAb,
- Cytomegalovirus (CMV) and Epstein-Barr virus (EBV)

9.8.7. Urine Pregnancy Testing

All female subjects must have a negative urine pregnancy test at randomization and each of the specified visits. A highly sensitive urine pregnancy test will be performed at the Randomization Visit (Day 1), On-Treatment Study Visits (Month 1 [Visit 3], Month 2 [Visit 4], Month 3 [Visit 5], Month 6 [Visit 6], Month 9 [Visit 7] and Month 12 [Visit 8])/ Discontinuation Visit.

9.8.8 Monitoring of SOC Therapeutic Level

Routine monitoring of subjects on VKA (INR) or heparin based therapy (Anti-FXa, aPTT) after randomization is performed locally and up through Month 3.

9.9. Physical Examination

Physical examination will be conducted for all scheduled visits except Randomization Visit and includes:

• Height and body weight

This may be performed by an Investigator or other healthcare provider designated by the Investigator.

• Vital signs including blood pressure, heart rate, and body temperature after resting in a sitting or supine position

Note: the appropriate cuff size base on arm circumference will be used.

Vital signs are captured for selected scheduled visits.

• An assessment of each of the relevant major body systems.

Information will be entered in the case report form, date of measurement, and measurement results for systolic blood pressure, diastolic blood pressure, pulse rate, body temperature, height, body weight, and body mass index (BMI).

9.10. Electrocardiograms

Not applicable.

9.11. Other Examinations

Not applicable.

10. OTHER ASSESSMENTS

A pediatric QOL questionnaire will be issued at randomization and at the end of the treatment period (Month 3, Visit 5) to assess such categories as: health and activities, feelings about themselves, relationships with others, and school behavior. Note the QOL can be filled out by EITHER a parent or the study participant. The same person should complete the QOL at Month 3.

PedsQL version 4.0, generic core scale will be used in the study. The Sponsor will provide a hard copy of the questionnaire. Data will be entered into the EDC.

The following questionnaires will be used:

- Adolescent (13-18) Self report
- Adolescent (13-18) Parent report
- Child (8-12) Self report
- Child (8-12) Parent report
- Young child (5-7) Self report
- Young child (5-7) Parent report
- Toddler (2-4) Parent report

11. STATISTICAL METHODS

11.1. General Statistical Considerations

All efficacy analyses will be based on the modified intention-to-treat (mITT) Analysis Set and will be performed based on the treatment group assigned at randomization.

Safety analysis will be performed using the Safety Analysis Set. Subjects will be analyzed according to actual treatment received.

All analyses for the Extension Period will be based on subjects who participate in the Extension Period and take only edoxaban in the Extension Period, in the specified analysis set, and will be summarized for the edoxaban treatment group. Data listings will be prepared for subjects who are randomized to the SOC arm, participate in the Extension Period, and do not switch to edoxaban right after the Month 3 Visit.

All confidence intervals will be descriptive and will be two-sided 95% confidence interval (CI), unless otherwise specified.

Unless otherwise specified, the baseline value of an efficacy variable for a subject is the last nonmissing measurement before the randomization, and the baseline value of a safety variable is the last non-missing measurement before the first dose of the study drug.

In general, missing data will not be imputed for the purpose of data analysis. No visit windows will be used for analysis.

Continuous variables will be summarized by the number of observations, mean, standard deviation, median, and minimum and maximum values. Categorical variables will be summarized using frequency counts and percentages. Summary statistics will be presented by treatment group.

There is no formal statistical interim analysis planned. However, after the first 50 subjects enrolled in the edoxaban treatment group and 25 subjects enrolled in the SOC treatment group complete the first 3-month treatment period, an interim assessments by IDMC of safety endpoints will be performed to allow for enrollment of subjects <1 year of age into study.

11.2. Analysis Sets

Randomized Analysis Set will include all subjects who sign the ICF and are randomized.

Safety Analysis Set will include all subjects in the Randomized Analysis Set who received at least 1 dose of study drug. Analysis will be based on the study drug the subject actually received.

mITT Analysis Set will include all subjects in the Randomized Analysis Set who received at least 1 dose of study drug. Analysis will be based on the study drug the subject was randomized to receive.

PK Analysis Set will include all subjects in the Safety Analysis Set who had at least 1 PK sample with measurable concentration.

PD Analysis Set will include all subjects in the Safety Analysis Set who had at least 1 measurable PD sample.

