2.3.3. Secondary Efficacy Endpoints

The secondary efficacy endpoints are:

- The combination of symptomatic TE in the systemic arterial or venous pathways including DVT, PE, stroke, intracardiac thrombus, SEE, and MI, and asymptomatic intracardiac thrombus identified by cardiac imaging, that occur from randomization to the Month 3 Visit.
- Deaths as a result of TE that occurs from randomization to the Month 3 Visit.
- All-cause mortality from randomization to the Month 3 Visit.
- The combination of symptomatic TE in the systemic arterial or venous pathways and asymptomatic intracardiac thrombus identified by cardiac imaging, which occur from the day after the Month 3 Visit to the date of the last dose of study drug plus 30 days for subjects who participate in the Extension Period.
- Deaths as a result of TE that occurs from the day after Month 3 Visit to the date of the last dose of study drug plus 30 days for subjects who participate in the Extension Period.
- All-cause mortality from the day after the Month 3 Visit to the date of the last dose of study drug plus 30 days for subjects who participate in the Extension Period.

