6.4.4. Month 3 (Visit 5; End of Main Treatment Period) Procedures

All randomized subjects including those that have discontinued treatment prior to Month 3 will have an EOT assessment at Month 3.

Note: if there was a symptomatic thrombotic event experienced by the subject prior to Month 3 documented by the appropriate imaging, a Month 3 echocardiogram is not necessary since the subject has met an event endpoint.

The following will be performed at this visit:

• Perform physical examination (Section 9.9) including:

Vital signs (BP, heart rate, and body temperature after resting in a sitting or supine position [Note: the appropriate cuff size base on arm circumference will be used.])

Height and body weight (may be performed by an Investigator or other healthcare provider designated by the Investigator).

- Review concomitant medications
- Count unused study drug tablets/bottles/syringe and calculate compliance
- Safety review for AEs/SAEs
- Review for symptomatic endpoint events (bleeding, symptomatic TE with appropriate imaging)
- Complete the QOL Questionnaire. Note: the QOL can be filled out by EITHER a parent or the study participant. The same person should complete the QOL at Month 3.
- Take samples for the following:

LFTs (ALT, AST, TBL, and ALP)

Serum creatinine and eGFR assessment

Hematology

Urine pregnancy test (for females of childbearing potential)

- Discretionary anti-FXa level and/or aPTT measurement for subjects on SOC with heparin and INR assessment for the subjects on SOC with VKA
- At the Investigator's discretion to extend the study, dispense edoxaban study drug medication and review dosing instructions per subject/parent(s)/guardian(s)'s request.
- Perform echocardiogram to evaluate presence of asymptomatic thrombosis. Note: if there was a symptomatic event experience by the subject prior to Month 3 documented by the appropriate imaging, a Month 3 echocardiogram is not necessary since the subject has meet an event endpoint.

6.5. Extension Period (beyond Month 3 – Month 6, 9, and 12; Visits 6, 7, and 8)

At the Investigator's discretion, study treatment can be extended up to 12 months. All subjects will be offered edoxaban treatment for the duration of the Extension Period based on the Investigator's judgment of the subject's potential thrombotic burden.

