11.3. Study Population Data

Subject disposition will be summarized by treatment group and in total for the Main Treatment Period and for the edoxaban treatment group for the Extension Period, respectively, for the Randomized Analysis Set. The number and percentage of randomized subjects who discontinued treatment prematurely will be tabulated by the main reason for discontinuation by treatment group for the Main Treatment Period and for the Extension Period.

The number of subjects for each defined analysis set will also be tabulated by treatment group as well as in total for the Main Treatment Period and for the Extension Period, respectively.

Subjects excluded from the analysis sets will be listed and summarized by treatment group and reason for exclusion for the Main Treatment Period and the Extension Period. A listing of all subjects with major protocol deviations will also be provided.

The demographic and baseline characteristics such as age, sex, race, height, weight, calculated BMI, type of underlying disease, taking concomitant aspirin or not at baseline, and primary and secondary prevention will be summarized descriptively for the mITT and Safety Analysis Sets. The demographic and baseline characteristics will also be summarized for subjects who participate in the Extension Period.

Study drug exposure and study duration will be summarized using descriptive statistics for the Safety Analysis Set by treatment group for the Main Treatment Period and the Extension Period. Edoxaban compliance will also be summarized using counts of tablets/ bottles. SOC compliance will be summarized by Percent time in therapeutic INR range for subjects who receive VKA or anti-FXa level for subjects who receive heparin.

Medical history will be summarized for the Safety Analysis Set. Prior medication will be summarized by treatment for the Safety Analysis Set. Concomitant medication will be summarized by treatment for the Safety Analysis Set for the Main Treatment Period and for the Extension Period.

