11.4.1.1. Secondary Efficacy Analysis

The TE stated in this Section, include symptomatic thrombi in the systemic arterial or venous pathways (DVT, PE, stroke, SEE, intracardiac thrombus, and MI), and asymptomatic intracardiac thrombus identified by cardiac imaging.

The following secondary efficacy endpoints will be summarized by treatment group using incidence, and annualized event rate for both the Main Treatment Period and the Extension Period, as well the rate difference between edoxaban and the comparator with the corresponding 95% CI for the Main Treatment Period. The incidence of each component will also be summarized by treatment group. This analysis will be based on CEC adjudicated results.

- The combination of symptomatic TE in the systemic arterial or venous pathways including DVT, PE, stroke, SEE, intracardiac thrombus, MI, and asymptomatic intracardiac thrombus identified by cardiac imaging that occur from randomization to the Month 3 Visit.
- Deaths as a result of TE that occurs from randomization to the Month 3 Visit.
- All-cause mortality occurring from randomization to the Month 3 Visit.
- The combination of symptomatic TE in the systemic arterial or venous pathways including DVT, PE, stroke, SEE, intracardiac thrombus, and MI, and asymptomatic intracardiac thrombus identified by cardiac imaging, which occur from the day after the Month 3 Visit to the date of last dose of study drug plus 30 days for subjects who participate in the Extension Period.
- Deaths as a result of TE that occurs from the day after the Month 3 Visit to the date of last dose of study drug plus 30 days for subjects who participate in the Extension Period.
- All-cause mortality which occur from the day after the Month 3 Visit to the date of last dose of study drug plus 30 days for subjects who participate in the Extension Period.

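### Main-period efficacy events are counted from randomization, but subjects who are never dosed are left out of the efficacy analysis set in an open-label trial

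*Combined protocol and SAP*

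**What the plan says.** **Analysis population.** Section 11.1: "All efficacy analyses will be based on the modified intention-to-treat (mITT) Analysis Set". Section 11.2 gives the membership rule for mITT: "will include all subjects in the Randomized Analysis Set who received at least 1 dose of study drug. Analysis will be based on the study" (quotation cut short here). Its labelling rule goes by assigned arm: "Analysis will be based on the study drug the subject was randomized to receive". The mITT set thus holds the same subjects as the Safety Analysis Set and differs only in how the arm is labelled.

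**Event window.** Section 11.4.1.1 counts the TE composite, including "asymptomatic intracardiac thrombus identified by cardiac imaging that occur from randomization to the Month 3 Visit". TE death has the same start and end, and Section 2.3.3 lists "All-cause mortality from randomization to the Month 3 Visit".

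**The full set.** Section 11.2 also states that "Randomized Analysis Set will include all subjects who sign the ICF and are randomized". Its stated use is in Section 11.3, where disposition is summarized "respectively, for the Randomized Analysis Set". I found no efficacy or sensitivity analysis on it.

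**Follow-up.** Section 6.4.4: "All randomized subjects including those that have discontinued treatment prior to Month 3 will have an EOT assessment" at Month 3.

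**The concern.** The clock and the analysis set do not match. An event can fall inside the endpoint window while the subject who had it falls outside the set. For bleeding the protocol does match them: Section 11.4.3.1 starts the primary endpoint at first dose and uses the Safety Analysis Set.

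The mismatch would matter little if never starting were unrelated to arm. Here it can be related. The trial is open-label (Section 3.1, with blinding not applicable in Section 5.1.3). Two routes to arm-dependent non-starting can be read from the text:

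- Section 5.6.3 lets the investigator end treatment on the judgment that even starting it is too hazardous. That judgment is made with the arm known.
- Under Section 5.2.4.1, a subject on a VKA who is assigned edoxaban stops the VKA the day before randomization and starts edoxaban only once the INR is 2.5 or lower. The protocol's VKA target is 2.0 to 3.0 (Sections 5.2.1.2 and 5.2.4.3), so some subjects can be expected above 2.5. I found no stated maximum for the wait.

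At stake is whether the comparison of TE and mortality, listed among the key secondary objectives in Section 2.1.2.1, is a comparison of everyone randomized. The direction of any bias cannot be predicted from the documents.

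**Working it through.** **Who is lost.** Setting the mITT rule beside the event window gives four cases:

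1. Dosed, event after dosing: in the set, event counted.
2. Non-fatal event before the first dose, dosed later: in the set, event counted, because the window opens at randomization.
3. Non-fatal event before the first dose, never dosed: out of the set, event lost.
4. Death before the first dose: out of the set, event lost.

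Only cases 3 and 4 are a problem. Never-dosed subjects without an event also drop out and change the denominator.

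**The plan's own figure.** Section 11.6 assumes major plus CRNM bleeding in 8.5% of 100 edoxaban and 10.3% of 50 SOC subjects, and gives a 95% CI for the risk difference of -11.8% to 8.2%. The unpooled Wald interval reproduces it:

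- d = 0.085 - 0.103 = -0.018
- SE = sqrt(0.085 × 0.915/100 + 0.103 × 0.897/50) = 0.0512
- d ± 1.96 × SE = -11.84% to +8.24%

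This figure concerns bleeding and does not change under the fix. It only fixes the method used below.

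**Size for efficacy.** The documents give no TE rate and no number of undosed subjects, so the counts here are assumptions: 100 and 50 randomized, 4 TEs among dosed edoxaban subjects and 2 among dosed SOC subjects. The risk difference is edoxaban minus SOC in percentage points, with the same Wald interval. That interval is crude at such counts and serves only for scale.

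| Assumed never-dosed subjects | mITT | Randomized Analysis Set | Shift |
|---|---|---|---|
| None | 4/100 - 2/50 = 0.0 (-6.7, 6.7) | same | 0.0 |
| 1 edoxaban, with TE | 4/99 - 2/50 = 0.0 (-6.6, 6.7) | 5/100 - 2/50 = +1.0 (-5.9, 7.9) | +1.0 |
| 1 SOC, with TE | 4/100 - 2/49 = -0.1 (-6.8, 6.7) | 4/100 - 3/50 = -2.0 (-9.6, 5.6) | -1.9 |
| 2 SOC, both with TE | 4/100 - 2/48 = -0.2 (-7.0, 6.7) | 4/100 - 4/50 = -4.0 (-12.4, 4.4) | -3.8 |
| 5 edoxaban, no TE | 4/95 - 2/50 = +0.2 (-6.6, 7.0) | 4/100 - 2/50 = 0.0 (-6.7, 6.7) | -0.2 |
| 5 SOC, no TE | 4/100 - 2/45 = -0.4 (-7.6, 6.7) | 4/100 - 2/50 = 0.0 (-6.7, 6.7) | +0.4 |

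Event-free exclusions hardly matter (at most 0.4 points for 1 to 5 subjects in one arm). An excluded event costs about 1 point in the edoxaban arm and about 2 in the smaller SOC arm.

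**The case against.** The case for leaving the plan alone has real weight.

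- **The interval is usually short.** Section 5.1.1 expects dosing on the day of randomization when a VKA-pretreated subject has an INR of 2.5 or lower, and Section 6.3 allows the first dose on Day 1 or Day 2. The INR wait concerns only VKA-pretreated edoxaban subjects above 2.5, and Section 5.2.4.1 permits heparin bridging meanwhile.
- **An excluded event may be unlikely.** Suppose 2 to 5 edoxaban subjects are never dosed and each carries a 2% to 4% three-month TE risk. The expected number of excluded TEs is 2 × 0.02 = 0.04 to 5 × 0.04 = 0.20. The chance of at least one is 1 - 0.98² = 4% to 1 - 0.96⁵ = 18%. It would be higher if the event itself prevents dosing, which cannot be quantified here.
- **The analysis is descriptive.** Sections 11.1 and 11.6 say the intervals are descriptive and the study is not powered. A 1-point shift is small beside about ±7.
- **Cases would be visible.** Exclusions are listed by arm and reason (Section 11.3), adverse events are collected from consent (Section 9.2), and all deaths are adjudicated (Section 7.1).

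These points limit the size of the problem but do not remove it. A listing does not put the event back into the estimate. Baseline characteristics are planned only for the mITT and Safety sets, so no planned table shows whether exclusions unbalanced the arms. The exploratory analyses in Section 11.4.1.2 change the window but stay under the mITT rule. A descriptive estimate can also be biased.

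**Conclusion.** The mismatch is in the text and is worth correcting, as a modest point about secondary endpoints. Its size depends on two quantities that the documents do not give: how many subjects are never dosed, and how many of them have an event. Under the assumed counts it is about 1 point per lost edoxaban event and about 2 per lost SOC event. It is zero if everyone is dosed.

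A reader might infer more than the documents support:

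- **That the randomized comparison is broken.** It is exposed to arm-dependent exclusion. Whether bias arises depends on the undosed subjects. The primary bleeding endpoint starts at first dose in a dosed set and is not affected.
- **That any event during the wait for INR removes the subject.** Only death before dosing, or an event after which dosing never starts, does so.
- **That the SOC arm has no such interval.** No INR wait is stated for subjects continuing a VKA there, but the Day 1 or Day 2 allowance is not limited to one arm.
- **That a lost event would be a quarter to a half of the edoxaban arm's events.** That share follows only if 2 to 4 TEs are assumed and one is already taken as lost.
- **That the as-randomized rule is at fault.** It is correct. The fault is the one-dose condition combined with a window that opens at randomization.

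**What to change.** In Section 11.1, and in the SAP that follows it, base the main-period TE composite, TE death and all-cause mortality on the Randomized Analysis Set by assigned arm, and keep the mITT analysis as supportive. Summarize baseline characteristics for the Randomized Analysis Set as well.

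State that never-dosed subjects are followed to the Month 3 assessment that Section 6.4.4 already requires for all randomized subjects. This needs explicit wording: Sections 5.6.1 and 6.4.3 describe subjects who stop treatment, and the follow-up visit in Table 17.1 is timed from the last dose or the Discontinuation Visit, so a subject who never starts has no clear path.

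The cost is small wording changes and follow-up of what should be few subjects. The planned sample size and the bleeding interval in Section 11.6 do not change. No dosing or transition rule needs to change for this point.

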11.3. Study Population Data

Subject disposition will be summarized by treatment group and in total for the Main Treatment Period and for the edoxaban treatment group for the Extension Period, respectively, for the Randomized Analysis Set. The number and percentage of randomized subjects who discontinued treatment prematurely will be tabulated by the main reason for discontinuation by treatment group for the Main Treatment Period and for the Extension Period.

The number of subjects for each defined analysis set will also be tabulated by treatment group as well as in total for the Main Treatment Period and for the Extension Period, respectively.

Subjects excluded from the analysis sets will be listed and summarized by treatment group and reason for exclusion for the Main Treatment Period and the Extension Period. A listing of all subjects with major protocol deviations will also be provided.

The demographic and baseline characteristics such as age, sex, race, height, weight, calculated BMI, type of underlying disease, taking concomitant aspirin or not at baseline, and primary and secondary prevention will be summarized descriptively for the mITT and Safety Analysis Sets. The demographic and baseline characteristics will also be summarized for subjects who participate in the Extension Period.

Study drug exposure and study duration will be summarized using descriptive statistics for the Safety Analysis Set by treatment group for the Main Treatment Period and the Extension Period. Edoxaban compliance will also be summarized using counts of tablets/ bottles. SOC compliance will be summarized by Percent time in therapeutic INR range for subjects who receive VKA or anti-FXa level for subjects who receive heparin.

Medical history will be summarized for the Safety Analysis Set. Prior medication will be summarized by treatment for the Safety Analysis Set. Concomitant medication will be summarized by treatment for the Safety Analysis Set for the Main Treatment Period and for the Extension Period.

